11.4. Appendix 4: Study Phases and Treatment States for Adverse Event Data

11.4.1. Study Phases

Study Phase	Definition
DHA-PQP only	Time of first administration of DHA-PQP to time of first dose of blinded study medication – 1 minute
Double blind	Time of first administration of blinded study medication to Day 180 visit
Open-label PQ phase, Non-Relapsers	Day 180 visit + 1 day to Day 180 visit+21 days for participants who do not relapse prior to Day 180 visit

Data collected outside of the above study phases, e.g. an AE with a start date after the Day 180 visit, for a participant not entering the open-label PQ phase, will be listed only.

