### **Premature Withdrawal of Study Treatment**

If a subject prematurely discontinues from study treatment for any reason or reaches the primary endpoint of relapse, they should continue to attend study visits to Day 180. The reason for withdrawal from treatment should be recorded in the electronic case record form (eCRF). Given the long half life of tafenoquine, the maximal pharmacodynamic effects such as potential hemolysis or methemoglobinemia may occur several days after completion of dosing. These data will be recorded, as they comprise an essential evaluation that needs to be done before discharging any subject from the study. Therefore, the investigator should continue following subjects for all protocol assessments, up to and including Day 180 whenever possible. The subject should be given appropriate rescue therapy according to local treatment guidelines if they develop a malarial recurrence (see Section 6.9.1.2).

Subjects should discontinue taking study treatment if they meet **any** of the criteria below:

- Intolerable AEs:
  - Any grade 4 AE or toxicity in the absence of compelling evidence that the AE is not related to investigational product(s)
- Clinically significant laboratory results considered by the investigator to warrant withdrawal from the study treatment
- Liver chemistry stopping criteria (refer to Section 5.4.1 and Section 12.2 Appendix 2)
- Hemoglobin stopping criteria: Given the hemolytic potential of TQ and PQ in subjects with G6PD deficiency, study specific hematologic stopping criteria will be employed (refer to Section 5.4.2)
- QTc stopping criteria (refer to Section 5.4.3)

When QT or hemolytic stopping criteria are met, this must be promptly reported by the investigator to GSK as a Serious Adverse Event (see Section 7.5)

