8.1.2 Overview of Planned Adverse Event Analyses

Counting of AEs will be based on the number of participants – not the number of AEs. For example, if a participant reports the same AE on three occasions within the relevant time interval, that AE will only be counted once. If a participant experiences the same AE (i.e. same preferred term) more than once, they are counted only once under the count for the preferred term. If a participant experiences more than one AE in a SOC, they will only be included once in the count for the SOC, but will appear in the count for each appropriate preferred term within the SOC. Therefore, the sum of the numbers of participants with each preferred term event within a SOC may exceed the total number of participants with at least one event. For the summary of AEs by maximum intensity, participants who experience the same event several times with different intensity will only be counted once with the maximum intensity.

The recurrence of *P. vivax* malaria and any associated signs and symptoms are recorded as Disease Related Events (DREs) and will not be included in the AE data displays, but will be listed separately.

Adverse Events will be summarized by treatment group and as specified in [Appendix 11](#) and presented in order of descending frequency. The tables presented using the Safety Population will be presented from administration of first study medication (including DHA-PQP) until Day 180.. The tables presented using the Safety OL population will be presented from Day 180 visit + 1 day until Day 180 visit + 21 days.

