11.6.4. Safety

Adverse Events
Adverse Events

All AEs reported up to and including the Day 180 visit (Day 195 visit for participants who do not relapse during the study) following enrolment of a participant into the study will be documented for participants in the Safety Population (or Safety OL Population).
 
These will be recorded and coded using the current version of Medical Dictionary for Regulatory Activities (MedDRA). All terms applied will be reviewed by a GSK physician prior to unblinding. If any malaria related coded terms are considered to have lost useful information in the coding step (e.g., if a verbatim term of 'Plasmodium vivax malaria' is mapped to 'malaria'), he/she will recommend a study-specific code, which will be documented. The process will be completed prior to study unblinding.
 
If the grade/intensity is missing for an AE, it will be considered severe/Grade 3 if an AE, or Grade 4 if an SAE and the participant is alive, or Grade 5 if an SAE and the participant dies (i.e. the highest intensity possible) for the summary of AEs by maximum intensity.
 
See Section 11.7.2 for more information on missing and partial dates.
 
Common AEs are those occurring in $\geq 5\%$ of participants in any treatment group.
 
The recurrence of malaria and any associated signs and symptoms are recorded as Disease Related Events (DREs) and will not be classified as AEs.

AE's of Special Interest

AEs of special interest are:
 
 Haematological events AEs with a system organ class (SOC) of "Nervous System Disorders" AEs with a SOC of "Psychiatric Disorders" AEs with a SOC of "Renal and Urinary Disorders" AEs with a SOC of "Hepatobiliary Disorders" 
Haematological events will be identified by GSK physicians, prior to unblinding, from a list of all unique preferred terms observed within the study.

Laboratory Parameters

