11.11.4. Safety Tables

Safety: Tables					
No.	Population	IDSL / Example Shell	Title	Programming Notes	Deliverable
Adverse Events (AEs)					
3.1	Safety	AE1	Summary of All Adverse Events by System Organ Class, Preferred Term and Treatment Phase	ICH E3 Add footnote: 'Events are ordered based on Total incidence'. Include total column. Include DHA-PQP only and Double-Blind treatment phases.	SAC
3.2	Safety OL	AE1	Summary of All Adverse Events by System Organ Class and Preferred Term (Open-Label, PQ Phase, Non-Relapsers)	Order events in descending order by incidence in TQ+DHA-PQP arm only. Include total column.	SAC
3.3	Safety	AE3	Summary of All Adverse Events During the Double-Blind Treatment Phase, by Preferred Term and Frequency	Order events in descending order by incidence in TQ+DHA-PQP arm only. Add footnote: 'Events are ordered based on incidence in TQ+DHA-PQP arm'. Include total column.	SAC
3.4	Safety	AE3	Summary of Common ($\geq 5\%$ in Any Treatment Group) Adverse Events During the Double-Blind Treatment Phase by Overall Frequency	ICH E3 Order events in descending order by incidence in TQ+DHA-PQP arm only. Add footnote: 'Events are ordered based on incidence in TQ+DHA-PQP arm'. Include total column.	Headline

Safety: Tables					
No.	Population	IDSL / Example Shell	Title	Programming Notes	Deliverable
3.5	Safety	AE15	Summary of Common ($\geq 5\%$ in Any Treatment Group) Non-serious Adverse Events During the Double-Blind Treatment Phase by System Organ Class and Preferred Term (Number of Subjects and Occurrences)	FDAAA, EudraCT Include total column.	SAC
3.6	Safety	AE5A	Summary of All Adverse Events During the Double-Blind Treatment Phase by System Organ Class, Preferred Term and Maximum Intensity	IDSL Order events in descending order by total incidence within each treatment group. Add footnote: 'Events are ordered based on total incidence within each treatment group'	SAC
3.7	Safety	AE3	Summary of Common ($\geq 5\%$) Grade 2-4 Adverse Events During the Double-Blind Treatment Phase by Overall Frequency	ICH E3 Include total column.	SAC
3.8	Safety	AE1CP	Summary of DHA-PQP-Related Adverse Events (as Reported by the Investigator) During the Double-Blind Treatment Phase by System Organ Class and Preferred Term	Order events in descending order by incidence in TQ+DHA-PQP arm only. Add footnote: 'Events are ordered based on incidence in TQ+DHA-PQP arm' Include total column.	Headline

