3.9	Safety	AE1CP	Summary of Blinded Treatment-Related Adverse Events (as Reported by the Investigator) During the Double-Blind Treatment Phase, by System Organ Class and Preferred Term	IDSL Order events in descending order by incidence in TQ+DHA-PQP arm only. Add footnote: 'Events are ordered based on incidence in TQ+DHA-PQP arm'	Headline

Safety: Tables					
No.	Population	IDSL / Example Shell	Title	Programming Notes	Deliverable
3.10	Safety	AE5A	Summary of Blinded Treatment-Related Adverse Events (as Reported by the Investigator) During the Double-Blind Treatment Phase, by Maximum Intensity, System Organ Class and Preferred Term	IDSL Order events in descending order by total incidence within each treatment group. Add footnote: 'Events are ordered based on total incidence within each treatment group'	SAC
3.11	Safety	AE3	Summary of Common (>=5%) Blinded Treatment-Related Grade 2-4 Adverse Events During the Double-Blind Treatment Phase, by Overall Frequency	ICH E3	SAC
3.12	Safety	AE1	Summary of Adverse Events During the Double-Blind Treatment Phase, with Onset On or Prior to Study Day 29 by System Organ Class and Preferred Term	Add footnote: 'Events are ordered based on Total incidence'	Headline
Serious and Other Significant Adverse Events					
3.13	Safety	AE1	Summary of Serious Adverse Events by System Organ Class, Preferred term and Treatment Phase	Add footnote: 'Events are ordered based on Total incidence' Include total column. Include DHA-PQP only and Double-Blind treatment phases.	Headline
3.14	Safety OL	AE1CP	Summary of Serious Adverse Events with Onset During the Open-Label, PQ Only Treatment Phase by SOC and Preferred Term	Order events in descending order by incidence in TQ+DHA-PQP arm only. Add footnote: 'Events are ordered based on incidence in TQ+DHA-PQP arm'. Include total column.	Headline
3.15	Safety	AE16	Summary of Serious Adverse Events by System Organ Class, Preferred Term and Treatment Phase (Number of Subjects and Occurrences)	FDAA, EudraCT Include total column. Include DHA-PQP only and Double-Blind treatment phases.	SAC

Safety: Tables					
No.	Population	IDSL / Example Shell	Title	Programming Notes	Deliverable

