3.16	Safety	AE1CP	Summary of Adverse Events During the Double-Blind Treatment Phase Leading to Withdrawal from the Study by System Organ Class and Preferred Term	IDSL Order events in descending order by incidence in TQ+DHA-PQP arm only. Add footnote: 'Events are ordered based on incidence in TQ+DHA-PQP arm' Include total column.	Headline
3.17	Safety	AE1CP	Summary of Adverse Events During the Double-Blind Treatment Phase Leading to Discontinuation from Study Treatment by System Organ Class and Preferred Term	IDSL Order events in descending order by incidence in TQ+DHA-PQP arm only. Add footnote: 'Events are ordered based on incidence in TQ+DHA-PQP arm' Include total column.	Headline
3.18	Safety	AE1CP	Summary of Adverse Events of Special Interest During the Double-Blind Treatment Phase by System Organ Class and Preferred Term	Order events in descending order by incidence in TQ+DHA-PQP arm only. Add footnote: 'Events are ordered based on incidence in TQ+DHA-PQP arm' Include total column.	Headline
3.19	Safety	AE3	Summary of protocol defined Hb SAEs During the Double-Blind Treatment Phase		SAC

Safety: Tables					
No.	Population	IDSL / Example Shell	Title	Programming Notes	Deliverable
3.20	Safety	AE3	Summary of Grade 3 and Grade 4 Adverse Events During the Double-Blind Treatment Phase by Preferred Term	Include Grade 3 and Grade 4 events only. Order events in descending order by incidence in TQ+DHA-PQP arm only. Add footnote: 'Events are ordered based on incidence in TQ+DHA-PQP arm' Include total column.	SAC
Laboratory: Chemistry					
3.21	Safety	LB1	Summary of Chemistry Data	Present values for all treatment groups and valid lab parameters at each visit.	Headline
3.22	Safety	LB1	Summary of Chemistry Changes from Baseline	ICH E3 Present change from baseline values for all treatment groups and valid lab parameters at each visit.	Headline
3.23	Safety	LB15	Summary of Worst Case Chemistry Results Relative to Normal Range Post-Baseline Relative to Baseline	ICH E3	SAC
3.24	Safety	SAFE_T1	Summary of Clinical Chemistry Laboratory Data Outside the Reference Range (F3)		SAC
Laboratory: Haematology					
3.25	Safety	LB1	Summary of Haematology Data	Present values for all treatment groups and valid lab parameters at each visit.	Headline
3.26	Safety	LB1	Summary of Hematology Changes from Baseline	ICH E3 Present change from baseline values for all treatment groups and valid lab parameters at each visit.	Headline

Safety: Tables					

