11.11.5. Safety Figures

Safety: Figures					
No.	Population	IDSL / Example Shell	Title	Programming Notes	Deliverable
Adverse Events					
3.1	Safety	AE10	Common ($\geq 5\%$ in Any Treatment Group) Adverse Events and Relative Risk During the Double-Blind Treatment Phase	IDSL	SAC
Laboratory					
3.2	Safety	LB11	LFT Profile Plots	
Only for subjects with >3 ULN in ALT or AST. Add footnote to this effect. The subject ID, treatment group, sex, age and race should be included as a header for each subject's plot. Include Alk. Phos, ALT, AST, Total Bili., and Indirect Bili.
	SAC
3.3	Safety	LB11	Haematology Profile Plots	
Only for subjects with a $>30\text{g/L}$ decline from baseline haemoglobin or found to be G6PD deficient Add footnote to this effect. The subject ID, treatment group, sex, age and G6PD status should be included as a header for each subject's plot. Parameters to include are haemoglobin, reticulocytes (if available), methaemoglobin and bilirubin results (total and indirect bilirubin on same plot)
	SAC

Safety: Figures					
No.	Population	IDSL / Example Shell	Title	Programming Notes	Deliverable
3.4	Safety	LB11	Clinical Chemistry Profile Plots	
Only for subjects change from baseline in urea or creatinine > 50% Add footnote to this effect.
 
The subject ID, treatment group, sex, age and race should be included as a header for each subject's plot.
 
Parameters to include are creatinine and urea (present the results relative to ULN).
	SAC
3.5	Safety	LB10	Distribution of Maximum LFTs by Treatment Group		SAC
3.6	Safety	LB7	LFT Shift from Baseline to Maximum Value		SAC
3.7	Safety	LB8	Matrix Display of Maximum LFT Values		SAC
3.8	Safety	SAFE_F1	Maximum Absolute Methaemoglobin Value Over 28 Days		SAC
3.9	Safety	LIVER14	Scatter Plot of Maximum vs. Baseline for ALT	IDSL	SAC
3.10	Safety	LIVER9	Scatterplot of Maximum ALT vs. Maximum Total Bilirubin	IDSL	SAC
Methaemoglobin					
3.11	Safety	SAFE_F2	Change from Baseline in Methaemoglobin over time	Display up to 28 days	SAC
Vital Signs					
3.12	Safety	LB9	Boxplot of Mean Arterial Blood Pressure by Timepoint and Treatment Group	IDSL Display LB9 includes the ULN and identifies subjects who have a value >2xULN. The ULN is not defined for arterial blood pressure, so this is not required. The figure should just include all of the data at each visit.	SAC

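### Adverse events after rescue count under the randomised arm up to Day 180 with no flag, and rescue is expected in 25 of 50 DHA-PQP-alone versus 7.5 of 50 tafenoquine participants

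*SAP*

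**What the plan says.** SAP 11.4.1 sets the double-blind phase as "Time of first administration of blinded study medication to Day 180 visit". SAP 8.1.2 adds: "The tables presented using the Safety Population will be presented from administration of first study medication (including DHA-PQP) until Day 180". It also counts participants, not events. Table 3.1 (all AEs), Table 3.13 (SAEs), Table 3.18 ("Summary of Adverse Events of Special Interest During the Double-Blind Treatment Phase by System Organ Class and Preferred Term") and Table 3.20 (Grade 3 and 4 AEs) follow this window, as does Figure 3.1, which shows common "Adverse Events and Relative Risk During the Double-Blind Treatment Phase".

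Protocol 6.9.1.2 gives relapsers an ACT plus 14 days of primaquine. Protocol 5.4 says that if a participant "reaches the primary endpoint of relapse, they should continue to attend study visits to Day 180". SAP 11.4.1 gives the primaquine taken by non-relapsers after Day 180 its own phase, with its own tables (3.2 and 3.14). No phase, table or flag marks the rescue course in relapsers.

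Relatedness (SAP 11.4.1.2) can be marked to DHA-PQP, to blinded medication, or to both. There is no rescue category, and a missing entry counts as related.

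**The concern.** DHA-PQP alone is the only arm that shows the AE background without an 8-aminoquinoline. It is also the arm in which most rescue primaquine will be given inside the reporting window. An AE caused by rescue raises incidence more in the control arm than in the tafenoquine arm, so tafenoquine looks better against control than it would otherwise. After Day 29 no planned all-cause table lets a reader see by how much. Flagging by SOC or by preferred term does not help, because AESIs are chosen by type of event ("Haematological events will be identified by GSK physicians, prior to unblinding" from a list of preferred terms) and not by timing relative to rescue.

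**Working it through.** **Inputs.** Protocol 9.2.1 assumes six-month relapse-free rates of 50% (DHA-PQP alone), 85% (primaquine) and 85% (tafenoquine), with 50 per arm and 10% withdrawal. The window is taken as 180 days. The documents give no distribution of relapse times and no AE rate after rescue.

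**The plan's own figure.** Expected relapses = 50 × (0.50 + 0.15 + 0.15) = 40, and 40/150 = 26.7%, as stated.

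**Participants rescued.** Control 50 × 0.50 = 25; tafenoquine 50 × 0.15 = 7.5. The gap is 0.35 of an arm. Primaquine also has 7.5, so tafenoquine versus primaquine is balanced at planned rates. AEs are counted per participant, so this is the figure that bears on the tables, and it needs no timing assumption.

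**Post-rescue share of the window.** With six-month relapse probability p, a constant hazard after a lag of L days gives share = (1 − L/180) × (1 − p/(−ln(1 − p))).

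| Lag (assumed) | DHA-PQP alone | Tafenoquine |
|---|---|---|
| 0 days | 1 − 0.50/0.6931 = 27.9% | 1 − 0.15/0.1625 = 7.7% |
| 28 days | 23.5% | 6.5% |
| 60 days | 18.6% | 5.1% |

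Allowing 10% exponential withdrawal at zero lag gives 27.4% and 7.6%. The ratio between arms stays at about 3.6 to 1. Time on the 14-day course itself is at most 0.50 × 14/180 = 3.9% versus 0.15 × 14/180 = 1.2%.

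**Size of the any-AE shift.** Let q be the chance that rescue causes an AE, and b the share of participants who would have an AE anyway. Someone already counted is not counted again, so the shift in tafenoquine minus control is −0.35 × q × (1 − b). The only primaquine AE rate in the documents is about 10% mild gastrointestinal upset on an empty stomach, improved by food (Protocol 4.5). Assume q of 5% to 10% and b of 20% to 40%:

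- smallest: 0.35 × 0.05 × 0.60 = 1.1 points
- largest: 0.35 × 0.10 × 0.80 = 2.8 points

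The shift is proportional to q. At q = 20% it would be 4.2 to 5.6 points.

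**Precision.** The 95% half-width for a difference at 50 per arm is 1.96 × √(2 × b(1 − b)/50): 15.7 points at b = 20% and 19.2 at b = 40%.

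**Table 3.12.** Under constant hazard, relapse by Day 29 is 10.6% versus 2.6%, a gap of 0.080. Over the same q and b the shift is 0.24 to 0.64 points, so this table is nearly free of the problem. It covers 29/180 = 16% of the window.

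**What a crude cut at rescue would do.** Mean pre-rescue follow-up is 180 × p/(−ln(1 − p)) = 129.8 days in control and 166.1 with tafenoquine. Suppose the AE hazard is identical in both arms and rescue has no effect. Over the window, let A = −ln(1 − b) be the cumulative AE hazard and H = −ln(1 − p) the cumulative relapse hazard. The chance of an AE before rescue is A/(A + H) × (1 − e^−(A+H)).

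- b = 20%: 14.6% control, 18.5% tafenoquine; artefact 3.9 points against tafenoquine
- b = 40%: 29.7% control, 37.2% tafenoquine; artefact 7.5 points against tafenoquine

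If half the AE hazard falls by Day 29, the artefact is still 2.6 to 4.8 points.

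**The case against.** The strongest reply is that much of the safety reporting already sits early in follow-up.

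- Table 3.12 takes AEs "with Onset On or Prior to Study Day 29" and is a headline deliverable.
- Table 3.30 and Figures 3.8 and 3.11 cover haemoglobin and methaemoglobin to 28 days, and Table 3.38 covers QTcF to 7 days. Protocol-defined haemoglobin SAEs are limited to the first 15 days (Protocol 7.5.1.1).
- Tables 3.8 to 3.11 are restricted to events related to DHA-PQP or blinded drug.
- Listed malaria symptoms with a positive slide are disease-related events, not AEs (Protocol 7.5.1.6).
- Listings 11, 13, 18, 20, 38 and 39 let a reader place individual events before or after relapse. With 150 participants this is feasible for SAEs.
- Safety is descriptive (Protocol 9.4.1), with no safety hypothesis.

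All of this stands, and it makes the point minor. It does not remove it. Table 3.12 has no SAE or AESI counterpart, the listings give case-by-case reconstruction and no summary, and relatedness has no rescue category.

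A reader might infer that 28% of control experience against 8% measures the bias. It does not. Those shares need a constant relapse hazard that the documents do not give, and AEs are counted per participant. Protocol 4.4 describes DHA-PQP as longer acting than artesunate, which makes later relapse, and so smaller shares, plausible.

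**Conclusion.** The point holds as a minor one. The all-cause AE, SAE and AESI displays to Day 180 mix pre-rescue and post-rescue events, with 50% of control and 15% of tafenoquine participants expected to be rescued at the planned rates. The post-rescue share of the window is about 19% to 28% versus 5% to 8%, from an assumed 60-day lag to constant hazard. The direction, towards tafenoquine against DHA-PQP alone, depends on rescue causing AEs. The any-AE shift of about 1 to 3 points rests on assumed q and b and is well inside the sampling error.

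Two stronger readings are not supported. One is that the to-Day-180 tables are wrong: counts by assigned arm over full follow-up are a legitimate summary, and the gap is only that no all-cause view separates rescue after Day 29. The other is that SAE or AESI comparisons are materially distorted: the documents give no rate from which a size could be derived, and gastrointestinal events, the only ones with a stated primaquine rate, are not AESIs (SAP 11.6.4).

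**What to change.** Keep every to-Day-180 table. Then:

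1. Add to SAP 11.4.1 a derived post-rescue flag: AE onset on or after the first rescue dose, using the rescue medication details that Protocol 6.9.1.2 already has recorded in the eCRF.
2. Show the flag in the AE and SAE listings (13, 18 and 20).
3. Add one by-arm summary of post-rescue AEs, SAEs and AESIs.
4. Give the pre-rescue view for any AE, SAE and AESI only in time-adjusted form: time to first event censored at first rescue dose, or exposure-adjusted rates split at Day 29. State that censoring at rescue is in effect censoring at relapse and may be informative.

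Do not produce crude pre-rescue versions of Tables 3.1, 3.13, 3.18, 3.20 or Figure 3.1. The shorter control follow-up (about 130 versus 166 days) would bias them against tafenoquine by more than the shift they are meant to show.

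The cost is one derived variable and a few extra displays. Nothing planned is removed, and trial conduct does not change.

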## Time and Events Table (Continued)

Procedures	Visit Day (Follow Up Period)									
	21	28	60	90	120	150	180	195 p (only for subjects who have not relapsed prior to Day 180)	Relapse	Withdrawal from study
Window	-/+3d	-3d, +15d	-16 d, +15d	-14d, +15d	-14d, +15d	-14d, +19d	-/+10d	Day 180 + 15d to 21d		
Efficacy Assessments										
Parasitological Assessment (blood smears)	x	x	x	x	x	x	x		x	x
Plasmodium PCR genotyping/sequencing									x	
Safety Assessments										
Concomitant Medication	x	x	x	x	x	x	x	x	x	x
Physical Examination	x	x	x	x	x	x	x		x	x
Vital Signs d	x	x	x	x	x	x	x		x	x
12-lead ECG e		x							x	x
Adverse Events	x	x	x	x	x	x	x	x	x	x
Serious Adverse Events	x	x	x	x	x	x	x	x	x	x
Dispense rescue treatment (ACT+PQ)									x	
Laboratory Assessments										
Hematology/Clinical Chemistry	x	x	x	x	x				x m	x m
Methemoglobin l	x	x	x						x	x
PK Sampling		x	x						x n	
Open Label Primaquine										
Dispense open label PQ –only for subjects who have not relapsed prior to D180							x			

Time and Event Table Notes:

- a) Blinded study treatment may be started on Day 1 or Day 2. If started on Day 2, blinded primaquine/placebo is given from Day 2-15.
- b) If a subject starts blinded study treatment on Day 2, the following assessments should be completed on Day 15: Concomitant medication, AEs/SAEs, methemoglobin, dispense blinded study treatment.
- c) Blood smears to be taken twice daily until two consecutive negative smears 6-12 hours apart.
- d) Vital signs include height and weight (screening only), blood pressure, temperature, heart rate and respiratory rate.
- e) ECGs will be done in triplicate on Day 1 (prior to DHA-PQP). Subsequent ECGs will be done as single ECGs unless prolonged QTcF is seen. ECG timings post baseline will be as follows: 1) Before the last of the three daily doses of DHA-PQP 2) 4 hours (window -1 to +2 hours) after last dose of DHA-PQP, 3) Day 7, 4) Day 28 and 5) relapse/withdrawal if within 28 days post-dose.
- f) Adverse events are recorded from the time of the first dose of study treatment.
- g) Serious adverse events are recorded from the time of consent in order to fulfil international regulatory requirements.
- h) G6PD phenotyping to be performed by suitable qualitative test (refer to SRM) and quantitative spectrophotometric analysis.

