11.3. Appendix 3: Assessment Windows

11.3.1. Definitions of Assessment Windows for Analyses

Analysis Set / Domain	Parameter (if applicable)	Target	Analysis Window		Analysis Timepoint
			Beginning Timepoint	Ending Timepoint	
miTT, PP, Safety	All	Day 1	Day 1	Day 1	Day 1
miTT, PP, Safety	All	Day 2	Day 2	Day 2	Day 2
miTT, PP, Safety	All	Day 3	Day 3	Day 3	Day 3
Safety	ECG	4 hours after last DHA-PQP dose	3 hours after last DHA-PQP dose	6 hours after last DHA-PQP dose	4 hours after last DHA-PQP dose
miTT, PP, Safety	All	Day 4	Day 4	Day 4	Day 4
miTT, PP, Safety	All	Day 5	Day 5	Day 5	Day 5
miTT, PP, Safety	All	Day 6	Day 6	Day 6	Day 6
miTT, PP, Safety	All	Day 7	Day 7	Day 7	Day 7
miTT, PP, Safety	All	Day 8	Day 8	Day 8	Day 8
miTT, PP, Safety	All	Day 9	Day 9	Day 9	Day 9
miTT, PP, Safety	All	Day 10	Day 10	Day 10	Day 10
miTT, PP, Safety	MetHB	Day 11	Day 11	Day 11	Day 11
miTT, PP, Safety	MetHB	Day 12	Day 12	Day 12	Day 12
miTT, PP, Safety	MetHB	Day 13	Day 13	Day 13	Day 13
miTT, PP, Safety	MetHB	Day 14	Day 14	Day 17	Day 14
miTT, PP, Safety	All except MetHB	Day 14	Day 11	Day 17	Day 14
miTT, PP, Safety	All	Day 21	Day 18	Day 24	Day 21
miTT, PP, Safety	All	Day 28	Day 25	Day 43	Day 28
miTT, PP, Safety	All	Day 60	Day 44	Day 75	Day 60
miTT, PP, Safety	All	Day 90	Day 76	Day 105	Day 90
miTT, PP, Safety	All	Day 120	Day 106	Day 135	Day 120
miTT, PP, Safety	All	Day 150	Day 136	Day 169	Day 150
miTT, PP, Safety	All	Day 180	Day 170	Day 190	Day 180
Safety OL	All	Day 180 visit + 15-21 days	Day 180 visit + 15 days	Day 180 visit + 21 days	Day 195

Note: Data collected after the nominal day 180 study visit, i.e. after the start of open label PQ for non-relapsers, will not be slotted to any visit up to and including the day 180 visit, regardless of the study day. Only the Day 195 visit window will be considered for slotting.

For all data summarised by visit, the nominal visit description will be used. Unscheduled and withdrawal visit data will be slotted into a scheduled visit window, but the data will only be included in summaries and figures if no scheduled visit exists within the same window. If there are multiple assessments within the same window which are not unscheduled visits, the earliest result will be used in the summaries and figures. If only unscheduled visits are included in the same window, the earliest of these results will be used in summaries and figures.

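### The open-label primaquine AE phase starts the day after the visit at which the drug is dispensed, so an AE after a same-day first dose misses the open-label tables

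*SAP*

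**What the plan says.** SAP 11.4.1 sets three phases for AEs. The double-blind phase is "Time of first administration of blinded study medication to Day 180 visit", and the open-label phase is "Day 180 visit + 1 day to Day 180 visit+21 days for participants who do not relapse prior to Day 180 visit". Data outside the phases go to listings alone. SAP 11.6.4 makes the Day 180 visit inclusive for the Safety population ("All AEs reported up to and including the Day 180 visit"). SAP 8.1.2 repeats the later start for the open-label tables ("The tables presented using the Safety OL population will be presented from Day 180 visit + 1 day until Day 180 visit + 21 days"), and SAP 6.1 uses the same window for the study population tables.

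On timing of the drug, the Day 180 column of the protocol's Time and Events Table carries the entry "Dispense open label PQ –only for subjects who have not relapsed prior to D180". The note to SAP 11.3.1 describes "Data collected after the nominal day 180 study visit, i.e. after the start of open label PQ for non-relapsers", which places the start of the drug at that visit.

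The other change of treatment is handled differently. The DHA-PQP-only phase ends at "time of first dose of blinded study medication – 1 minute", and SAP 11.7.2.1 adds a rule for AEs on that date whose start time is unknown.

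**The concern.** The Safety OL population was added to the SAP (section 2.1) to summarise AEs in men who had not relapsed and went on to open-label primaquine. A phase that opens the day after the drug is dispensed can leave out the first day of dosing. An AE that follows a first dose taken at the visit would then be missing from the tables meant to show it, and could be tabulated under the randomised drug, which was given about six months before.

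Attribution would not reliably correct this. SAP 11.4.1.2 lets an AE be related to DHA-PQP, to blinded medication, or to both, with no option for open-label primaquine, and it counts a missing relationship as drug-related. Several of the affected displays (Tables 3.4, 3.9, 3.13 and 3.14) are headline deliverables. With 50 men per arm, the 5% threshold for a common AE is 3 men, so one misplaced event (2 percentage points) can carry a term across it.

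**Working it through.** **Where a visit-day AE lands.** Take a man who has not relapsed, receives his first open-label dose at the Day 180 visit, and has an AE that evening.
- If phases are assigned by date, the AE is on the visit date, so it is double-blind.
- If the visit is read as a clock time, the AE comes after the double-blind phase and before the open-label phase, so it is only listed.
- On either reading it cannot enter Table 3.2 or 3.14. SAP 11.6.4 favours the first reading.

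**Men exposed on that day.** The inputs are in Protocol 9.2.1: 50 men per arm, relapse-free rates of 85% (tafenoquine), 85% (primaquine) and 50% (DHA-PQP alone), and 10% withdrawal. The plan's own figure reproduces: 50 × (0.15 + 0.15 + 0.50) = 40 relapses, and 40/150 = 26.7%.

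Men starting open-label primaquine = 50 × 0.90 × relapse-free rate. The documents give no first-day AE rate, so r below is an assumption, shown from 1% to 10%. The nearest figure (Protocol 4.5) is about 10% with mild gastrointestinal upset when primaquine is taken on an empty stomach. It is not tied to a single dose, and Protocol 6.8 has the open-label drug taken with food, so 10% is an upper illustration.

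| | Tafenoquine | Primaquine | DHA-PQP alone |
|---|---|---|---|
| Men starting open-label drug | 38.25 | 38.25 | 22.5 |
| Men with a misplaced AE, r = 1% | 0.38 | 0.38 | 0.23 |
| r = 5% | 1.9 | 1.9 | 1.1 |
| r = 10% | 3.8 | 3.8 | 2.3 |

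From this mechanism alone, tafenoquine minus DHA-PQP alone is (38.25 − 22.5) × r / 50, or 0.3, 1.6 and 3.2 percentage points. Tafenoquine minus primaquine is zero. These are ceilings, because SAP 8.1.2 counts a man once per preferred term and a man who already had that event adds nothing.

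**Rescue primaquine in the same phase.** Under Protocol 6.9.1.2 a man who relapses receives an ACT plus primaquine 0.5 mg/kg for 14 days, and AEs during that course are double-blind under SAP 11.4.1. Counting rescue courses and same-day Day 180 doses together:
- First 0.5 mg/kg doses inside the double-blind phase: 6.75 + 38.25 = 45 in each active arm, and 22.5 + 22.5 = 45 in DHA-PQP alone.
- Dose-days inside that phase: 6.75 × 14 + 38.25 = 132.75 in each active arm, and 22.5 × 14 + 22.5 = 337.5 in DHA-PQP alone. This assumes every rescue course is completed before the Day 180 visit.

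**The case against.** The strongest reply is that no passage says the first dose is swallowed at the visit. The table says the drug is dispensed, and Protocol 6.8 says that men who complete the visit will then be treated. Dosing on Days 181 to 194 gives 14 days before the Day 195 visit and agrees with the SAP's later start. This stands in part: same-day dosing is an inference. But Days 180 to 193 fit equally well, the same table uses the same verb for DHA-PQP and blinded drug that are taken on the day, and "i.e. after the start of open label PQ for non-relapsers" in SAP 11.3.1 points to the visit. A split at the actual dose is right on either reading.

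Second, the consequences are limited. Safety is summarised descriptively (Protocol 9.4.1), Table 3.12 stops at onset by Study Day 29, and all AEs appear in listings. That stands, and it is why the point is small.

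A reader might also infer that the boundary biases the blinded AE comparison against tafenoquine, because more tafenoquine than DHA-PQP-alone men reach Day 180 without relapse. The documents do not support that. The primaquine arm is planned at the same relapse-free rate, so it is affected equally. Against DHA-PQP alone, rescue courses equalise the number of first 0.5 mg/kg doses in the double-blind phase and put more dose-days in the DHA-PQP-alone arm.

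**Conclusion.** The boundary is inconsistent with the SAP's own view of when open-label primaquine starts. If dosing begins on the visit day, AEs after that dose are lost from Tables 3.2 and 3.14 and, phased by date, counted under the blinded arm. About 38, 38 and 22.5 men per 50 (tafenoquine, primaquine, DHA-PQP alone) would be exposed that day, assuming the planning rates and 10% withdrawal in every arm. The number of AEs misplaced cannot be fixed from the documents. At an assumed 1% to 10% it is at most about four men in any arm. Efficacy is unaffected, and neither the direction nor the size of any net bias between arms is established. This is a small correction to the safety tables.

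**What to change.** In SAP 11.4.1, for men who have not relapsed and take open-label primaquine, end the double-blind phase one minute before the first open-label dose and start the open-label phase at that dose. Leave the end of the double-blind phase at the Day 180 visit for everyone else. Align the windows in SAP 6.1 and 8.1.2.

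If the dose time or the AE onset time is not available, assign AEs with onset on the date of the first open-label dose to the open-label phase, a tie-break like the one in SAP 11.7.2.1. This will move a few AEs that began earlier that day, which is acceptable if stated.

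Optionally, flag double-blind AEs with onset after rescue primaquine, so that the larger source of non-randomised primaquine in that phase is also visible.

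The cost is one definition and two matching sentences, settled before unblinding. Protocol 6.8 says administration of the open-label drug is recorded in the eCRF but does not say that date and time are, so the data fields should be checked. No new collection is needed if the dose date is held.
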